For the intervention, approximately 102 Platoon Leadership Teams (PLTs) from 7-8 battalions will be targeted for leadership training and testing of Hypothesis 1. For Service Member participation, based on communications with our JBLM partners, we expect about 30% of the total population ($N=5200$) to participate ($n=1560$) at baseline. In addition, based on both our own experience and on those same communications, we expect about 20% attrition at the second data collection, owing largely to individual change in duty stations, remote training, deployments, etc. Thus, we anticipate 1245 soldiers to participate in the study data collection at baseline and at the 6-month follow-up for Hypotheses 2, 3 and 4.

We will work with command teams to avoid data collection, when possible, that would be timed during large deployments or other similar anticipated events. Participation in the training is mandatory, though allowing our researchers to use data collected in association with the training (e.g., test scores, reaction) will be consented. However, the increased sample size will allow our team greater flexibility in dealing with these issues should they arise.

b. Inclusion and Exclusion Criteria

The inclusion criteria for soldiers is to be currently serving Active Duty in one of the targeted battalions, and in positions of platoon leader or below. For the leader training, we will target the platoon leaders and platoon sergeants. We will work with senior leadership to identify these individuals.

c. Vulnerable Populations

No individuals who are known to be members of a vulnerable population will be enrolled. We will not identify subjects on whether they are members of a vulnerable population. In other words, we will not collect any information about subjects' status as part of any vulnerable populations, including prisoners, pregnant woman, children, neonates, and/or adults lacking capacity.

d. Setting

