All study staff dealing with both participants and/or data will have completed sanctioned Human Subject Research training. The PI and Project Manager both have experience with DoD-regulated research and reviewed these regulations with the DoD Science Officer after the grant was awarded. They will both be responsible for training any new study staff with regard to these specific DoD regulations.

b. Survey Measures

We will collect sociodemographic data and military experience, including military work history, combat exposure and deployment history. Our survey outcome measures will map on to our hypotheses to ensure we can evaluate between- and within-group effects. We will also ask which specific unit to which they are currently assigned so we can nest data within units and account for unit-level similarities (see Statistical Analysis below). Some of the hypotheses include data that are not from the surveys, such as training data (pre- and post-tests) (see Hypothesis 1), but we will track that information as well and merge with survey data. Table 1 includes a summary of proposed measures, sources, and when and from whom they will be collected. All proposed measures have been used in previous research and are psychometrically sound. A list of individual surveys items are included in our submission.

Hypothesis 2 will be evaluated with a measure assessing the leader's support for resilience within their unit. This measure, commensurate with previous work we have done (e.g., Family-Supportive Supervisor Behaviors and Sleep Leadership), will be developed based on tenets of the intervention. It will be measured from the perspective of the subordinates (e.g., "My platoon leadership team supports resilience in our unit"). Before reporting any

findings on Hypothesis 2, we will examine the psychometric properties of the adapted measure to ensure reliability and validity.

The bulk of the survey will be comprised of measures that assess Hypotheses 3 and 4. Hypothesis 3 is specific to perceptions around resilience factors such as social connectedness, resilience, and emotional regulation, whereas Hypothesis 4 is specific to perceptions around resilience-related outcomes including psychological, physical health, and well-being.

Table 1. Summary of Survey Measures

Concept	Measure	Reference	# of Items	When collected*	Who*	Hyp.
Leader Training Data	Leader reactions to training	Adapted from [name] et al. (2011)	3	T	PLT	1

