	Knowledge of resilience leadership	Adapted from [name] et al. (2011)	3	T	PLT	1
Resilience-supportive Behaviors	RSLB measure adapted from VSSB and FSSB (Service Member's Ratings of Leaders)	Adapted from Perry et al. (2018) and [name] et al. (2009, 2013)	3-5	S	SM	2
	Perceived Leader Effectiveness	Adapted from Ragins 1989 by WRAIR	5	S	SM	2
	General Supervisor Support	Yoon & Lim (1999)	3	S	SM	2
Emotion Regulation	Reappraisal and Emotion Suppression	Gross & John (2003)	10	S	SM	3
Resilience	Brief Resilience Scale	Smith et al. (2008)	6	S	SM	3
	CD-RISC (Brief Connor-Davidson Resilience)	Campbell-Sills & Stein (2007)	10	S	SM	3
Social Connectedness	Thwarted Belongingness Subscale	Hill et al. (2015).	5	S	SM	3
	Brief Loneliness Scale	Hughes, et al. (2004)	3	S	SM	3

Psychological Health	K6 Psychological Distress	Kessler et al. (2002)	6	S	SM	4
	Functional Impairment (WRAIR)	Herrell et al. (2014)	13	S	SM	4
	Perceived Stress Scale (PSS)	Cohen et al. (1983)	4	S	SM	4
	PTSD (PCL-5)	Price et al. (2016)	4	S	SM	4
	Dimensions of Anger (DAR-5)	Forbes et al. (2014)	5	S	SM	4
Physical Health	Sleep Problems	Jenkins et al. (1988)	4	S	SM	4
	General Perceived Health	Hobfoll et al. (2012)	4	S	SM	4
	Chronic Pain	Mattacola et al. (1997)	1	S	SM	4
	Alcohol misuse (AUDIT-C)	Bush et al. (1998)	3	S	SM	4
Unit Cohesion	Unit Cohesion	Williams et al. (2016)	8	S	SM	4
Demographics	Brief Combat Exposure	WRAIR		T S	PLT, SM	
	Unit info, age, rank, gender, Relationship Status, # of Children,			T S	PLT, SM	
	Years in military, deployment history,					
	Months in platoon					

*NOTE: T = Training; S = Survey; PLT = Platoon Leadership Team; SM = Service Member

c. Sharing of Results with Subjects

We currently do not have plans to share results with participants participating in the survey. Leaders in the treatment group will receive the results of their pre- and post-test on the training. Results of the study will be shared with the leadership at JBLM, but only at an aggregate level.

8. Data Analysis

a. Statistical Plan and Data Analysis

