The data for this study will be generated from a randomized controlled trial with all participating leaders and soldiers (in non-support units) within the participating units randomly assigned (by battalion) to either an intervention or usual practice control condition. Standard general linear and generalized linear mixed model approaches for clustered designs (i.e., hierarchical linear models, multilevel models; Murray, 1998; Murray, Varnell, & Blitstein, 2004) will be used for data analysis for Hypotheses 2-4 to account for the clustered nature of the data. As these models are now widely used and understood and are available in numerous statistical software packages, our discussion here on the specifics of these analyses will be brief. For each hypothesis, link functions for these models will be determined by the scaling of each outcome variable. As study implementation (i.e., intervention-related and data collection activities) will occur at the level of the platoon within brigades, platoon-level random effects will be included in these statistical models. The evaluation of Hypothesis 1 will focus on leaders in the intervention condition providing a point estimate and confidence interval for the usefulness of the training and the change in training-related knowledge from pre- to post-training. Hypotheses 2-4 will focus on differences in the key study outcomes between the intervention and usual practice conditions for soldiers. For these latter models, we will use the outcome variable at baseline as a predictor in the model to adjust for unexpected imbalance across conditions and to increase the statistical power for and precision of parameter estimates (cf. Bodner & Bliese, 2018). Finally based on planned preliminary data analyses, the recruitment wave (i.e., block), rank, gender, unit type, marital status, and mental health symptoms of soldiers may be used as predictors in the statistical models to further increase statistical power or eliminate potential intervention effect bias. Of interest in these latter models is the direction, magnitude, and statistical significance of the parameter corresponding to the intervention condition indicator. As needed, depending on attrition and missing data, this basic generalized linear mixed model will be extended in the analysis of the study hypotheses as mentioned below (e.g., multiple imputation for missing predictor variable values, FIML estimation for missing outcome variable values).

b. Power Analyses

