This section documents the power analyses we conducted for the planned analyses for Hypotheses 1-4.

Key factors for the power analysis are the likely size of the intervention effect and the degree of non-independence, quantified as an intra-class correlation, as leaders and soldiers are nested in platoons, given the expected number of platoons discussed above. Prior research with platoon-level implementation (e.g., Adler, et al., 2009; Adler, et al., 2015a; Adler, et al., 2015b) indicates platoon-level random effects are often considered small in size (e.g., ICCs $< .04$, except when the outcome involves a platoon-level construct such as cohesion). Although small, it is important to include these effects in the analysis models for the study hypotheses and to incorporate these random effects into the power analyses for the study hypotheses. In the power analyses, we assumed an ICC of .04 for the platoon-level random effects.

Hypothesis 1 assesses the perceived usefulness of the training as rated by the leaders that participate in the training. Our prior research involving similar leadership training (i.e., SERVe) indicated that 81% of the 928 trained leaders rated it as good or excellent and 95% rated it as useful to extremely useful for their work. Hypothesis 1 also assesses the increase in leader knowledge of the training material. Prior research indicates that these increases in knowledge are large [e.g., $d = 3.31$ in Anger, et al., unpublished; $d = 1.23$ in [name], et al. (2011)]. Using

the smaller of these effect size estimates for the power analysis for H1, we estimate power to be .99 in the current study.

Hypothesis 2 assesses the effect of the intervention on the soldiers' perceptions of their leaders on the targeted intervention behaviors. Estimates of the effect of similar leadership interventions on subordinate perceptions of targeted leadership behaviors indicate small positive effects [e.g., $d = .27$ in Crain, et al. (2018); $d = .39$ in Odle-Dusseau, et al. (2016)]. Using the smaller of these effect size estimates for the power analysis for H2, we estimate power to be .96 in the current study.

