Missing data intermittently during the study and/or dropouts are inevitable and an issue faced by all longitudinal studies, although recent evidence indicates relatively low levels of attrition for randomized trials in a military context (Adler, Williams, et al., 2015). There is no consensus, however, on the optimal analytical strategy to analyze missing data. Using the standard missing data taxonomy (Rubin, 1987), we will follow the recommendations made by Nich and Carroll (1997, 2002) and conduct intent-to-treat analyses using three strategies. In the first strategy we will extend the multiple imputation method of Little and Yau (1996) to allow for non-monotone missing values, which could occur intermittently during the study period. Monotone missing patterns require subsequent variables to be missing once a variable is missing. We will impute unobserved outcomes based on study condition, observed subject-level covariates at baseline and observed follow-ups. Inferences will be made on imputed datasets using Rubin's method (Barnes, Lindborg, & Seaman, 2006; Rubin, 1996). Our second analytical strategy will consider selection models and pattern-mixture models (Michiels, Molenberghs, Bijnens, Vangeneugden, & Thijs, 2002) based on different factorization of the joint distribution of the response variables and the missing patterns. As different strategies require different assumptions for the estimated treatment effects to be unbiased and some assumptions are not testable, comparisons of these strategies serve mainly as sensitivity analyses of their influence on the estimated key parameters of each Aim. A third strategy will consider the use of Full Information Maximum Likelihood methods in the analysis of incomplete data as implemented in several software programs (e.g., Mplus; Muthén & Muthén, 2007). As mentioned in the prior section, this study is adequately powered for an attrition rate of 20%.

9. Privacy, Confidentiality, and Data Security

Confidentiality:

- All devices that can link to OHSU or house OHSU data are required to have Symantec Whole Desk Encryption software installed. All data will be stored on secure, password protected servers.
- Methods of sharing data will NOT include the use of email or thumb drives, but rather by IRB approved methods, such as Box.com, which is sanctioned by OHSU's IRB.

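### Section 8c imputes missing outcomes without a platoon term that the section 8a model contains, so the pooled standard error is about 4–7% too small at ICC .04

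*Combined protocol and SAP*

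**What the plan says.** Section 8c (Missing Data and the Application of Intent-to-Treat) plans intent-to-treat analyses by three routes: MI, selection or pattern-mixture models, and full information maximum likelihood (FIML). For MI it lists the imputation inputs: "We will impute unobserved outcomes based on study condition, observed subject-level covariates at baseline and observed follow-ups". Results are pooled by Rubin's rules. No section adds a platoon term; the optional covariates in section 8a include unit type but not platoon identity.

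The analysis model does have one. Section 8a, on Hypotheses 2–4, says "platoon-level random effects will be included in these statistical models". Section 8b adds that "it is important to include these effects in the analysis models for the study hypotheses" and assumes an ICC of .04, treated as an upper range "except when the outcome involves a platoon-level construct such as cohesion". Section 7b asks soldiers for their unit "so we can nest data within units and account for unit-level similarities", and Table 1 records it in a row beginning "Unit info, age, rank, gender, Relationship Status".

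On the division of labour, section 8a offers as an example "multiple imputation for missing predictor variable values, FIML estimation for missing outcome variable values". Section 8c lists MI first and FIML third. Neither section says which is primary for missing outcomes.

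**The concern.** An imputation model should carry at least the structure of the analysis model applied afterwards. Here the analysis assumes that soldiers in one platoon resemble each other, while the imputation treats missing soldiers as independent given arm and covariates. There is one follow-up survey, so a soldier who misses it has no follow-up data to carry platoon information. The imputed value therefore shares no platoon effect with platoon-mates beyond what baseline data convey. The platoon variance estimated from the completed data is too low, and Rubin's rules do not restore it.

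At stake are the intervals and tests for Hypotheses 2–4 if MI carries them. The comparison of strategies in section 8c also suffers: a difference in standard error between MI and FIML would partly reflect the omitted platoon term and not the missingness assumptions being probed.

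**Working it through.** **Inputs from the documents.** Baseline n = 1560, 1245 at both waves, 20% attrition (section 5a); platoon ICC .04 (8b); 11 battalions (section 4); "approximately 102 Platoon Leadership Teams (PLTs) from 7-8 battalions will be targeted for leadership training" (5a).

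**Assumptions.** Two-sided .05; arms split 7.5:3.5, from 7–8 of 11 battalions trained. The platoon count can be read two ways:
- A: 102 platoons in all, 1560/102 = 15.3 soldiers each.
- B: 102 trained platoons only, so about 102 × 11/7.5 = 150 in all, 1560/150 = 10.4 each.

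**Reproducing the plan's power.** Under A, completers per platoon are 1245/102 = 12.2, the design effect is 1 + 11.2 × .04 = 1.448, and effective n = 1245/1.448 = 860. SE = 1/√(860 × .682 × .318) = .0732. For d = .27, .205 and .217, power is .958, .799 and .842, against the stated .96, .80 and .84. Reading A therefore fits the plan's figures, given the assumed split.

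**Formula for the shortfall.** With m soldiers per platoon, ICC ρ and missing fraction f, up to a common factor and with soldiers missing at random within platoons:
- True variance: [1 + (m−1)(1−f)ρ]/(1−f).
- Rubin total when platoon is ignored: [1 + (m−1)ρ(1−f)²] + f/(1−f). Only pairs with both outcomes observed still share a platoon effect, so the completed-data ICC is about .64 × .04 = .026.

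Reading A: true 1.4576/.8 = 1.822; Rubin 1.366 + .25 = 1.616; SE ratio √(1.616/1.822) = .942, or 5.8% too small. Reading B: true 1.626; Rubin 1.491; ratio .957, or 4.3% too small. If whole platoons are lost, (1−f) leaves the true-variance numerator and (1−f)² becomes (1−f) in the Rubin term. The ratios are then .932 (A) and .950 (B).

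**Simulation.** 8,000 null trials per case. A used 70:32 platoons of 15; B used 102:48 platoons of 10. Battalion variance was zero. The baseline outcome had the same ICC and correlated .5 with follow-up at both levels. Outcomes were missing completely at random, by soldier or by whole platoon. MI used 20 imputations; the analysis was a REML mixed model on arm, baseline and a platoon intercept. SE ratio is mean SE over empirical SD; shortfall is one minus the MI ratio over the FIML ratio.

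| Case, ICC .04 | MI as written: SE ratio, type I | FIML: SE ratio, type I | Shortfall | Mean SE: MI as written → multilevel MI |
|---|---|---|---|---|
| A, by soldier | .948, .062 | 1.004, .051 | 5.6% | .0606 → .0641 |
| A, by platoon | .922, .067 | .986, .050 | 6.5% | .0624 → .0670 |
| B, by soldier | .978, .054 | 1.017, .046 | 3.8% | .0585 → .0608 |
| B, by platoon | .946, .062 | .993, .052 | 4.7% | .0598 → .0630 |

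Monte Carlo error is about .008 on each SE ratio and .003 on type I error. In A, multilevel MI gave SE ratios of 1.003 and .986 and type I error of .051 in both cases. The mean arm estimate was within .0015 of zero throughout. Two further simulations agree. One, with 900 trials per case and soldier-level loss, gave shortfalls of 5.1% (102 platoons) and 3.4% (150). The other, with 1,500 per case, gave MI/FIML ratios of .945 and .933 (A) and .963 and .948 (B).

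**Sensitivity to assumed values.**
- ICC .02: 3.2–4.1% in A, 2.0–2.8% in B; type I .052–.057.
- ICC .10, as might apply to cohesion: 9.8–11.1% in A, 7.6–9.0% in B; type I .065–.078.
- Baseline correlation .3 or .7 (A, by soldier): MI/FIML ratio .945 and .944, so no change.

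**If unit is read as a subject-level covariate.** Table 1 permits this. Entered as platoon indicators (ICC .04, loss by soldier), it errs the other way: SE ratio 1.137 and type I .026 in A, 1.178 and .022 in B. Indicators also cannot impute a platoon with no observed outcomes.

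**The case against.** The strongest reply is that section 8a introduces its missing-data methods as extensions of the mixed model, which has the platoon effect, and that unit is collected for nesting. On that view the sentence in 8c is shorthand. Section 8a's example also gives missing outcomes to FIML, which is well calibrated here. Nothing makes MI primary, and 8c uses the comparison of strategies mainly for sensitivity. The plan describes platoon ICCs as often below .04, and at .02 the error is small. Finally, battalions are randomized, and a small battalion variance would matter as much. With an assumed battalion ICC of .0015 and 1245/11 = 113 completers per battalion, the design effect is about 1.448 + 112 × .0015 = 1.616. A platoon-only model sees about 1 + 11.2 × .0415 = 1.465, and √(1.465/1.616) = .952, again about 5% too small.

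Much of this stands as a limit on size: only MI is affected, the arm estimate showed no bias, and battalion variance is a separate problem that this change does not solve. It does not remove the point. Section 8c gives a positive list of inputs, and the cross-reference in 8a leads back to that list without adding a cluster term. FIML for outcomes is only an example in 8a, while 8c says plainly that outcomes will be imputed and used for inference.

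**Conclusion.** The concern holds. Followed as written, the imputation rule in section 8c does not match the section 8a model and understates the MI standard error by about 4–7% at ICC .04 and 20% attrition. Type I error is about .06–.07 if there are 102 platoons in all, and .054–.062 if there are about 150. The upper end needs loss of whole platoons. These figures assume zero battalion variance, outcomes missing completely at random, and the platoon counts and allocation set out above; the absence of bias was checked only under the null. The effect is modest and confined to one of three strategies, but it would grow for cohesion if that outcome's ICC is higher. It is worth correcting before analysis.

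**What to change.** In section 8c, state that outcomes are imputed with a multilevel model containing arm, the baseline outcome, the subject-level covariates and the same cluster random effects as the section 8a model (platoon at least), entered as random effects and not as indicators. In 8a and 8c, state whether MI or FIML is primary for missing outcomes; this is a pre-specification matter that the main point does not depend on.

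The cost is one sentence in each section and a multilevel imputation routine. MI intervals become about 4–7% wider at ICC .04 (.0608/.0585 = 1.039 up to .0670/.0624 = 1.074). That width is right only if there is no battalion-level variance, which needs to be dealt with separately.

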- Any contact information, including mailing address, email and phone numbers for participants will be kept separate from any files containing survey data. We will only have this contact information from platoon leaders and unit POCs (not soldiers). Only a few key staff members will have access to these files with contact information, generally those who need to interact with participants for incentive payments or for reminders to complete a survey or training.
- If there is a reasonable expectation of harm to self or others, staff are expected to break confidentiality by reporting this to the proper authorities. This information is included in the Informed Consent.
- We have included a statement in the Informed Consent stating that representatives of USAMRMC (DoD) may review our study records to ensure we are compliant with our research protocols.

Disposition of Data:

- Electronic data will be stored primarily on the secure OHSU servers, which is encrypted and password protected.
- Any hard copies of data will be kept in a locked file cabinet in the project office, which is also locked when no one is present.
- De-identified data will be kept indefinitely on the secure servers at OHSU.
- Any contact information for participants will be destroyed at the end of the project.
- The project manager will be primarily responsible for ensuring data are secure and protocols are followed by all approved and trained staff.
 - We will have a data sharing agreement that details these protocols to ensure the confidentiality and integrity of the data. A signed copy stating they will comply with these protocols must be on file with the project manager before an individual is granted access to data, as well as a valid reason for having access (e.g., a paper proposal).
 - All individuals who will have contact with data and/or participants will have a copy of a record of Human Subjects training on file.

10. Provisions to Monitor the Data to Ensure the Safety of Subjects

We will prepare this if the study is deemed to be more than Minimal Risk.

11. Risks and Benefits

a. Risks to Subjects

Foreseeable risks:

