Efforts will be made to minimize risks associated with this study. Minimal potential risks for participation include breaches of confidentiality associated with data collected for research purposes. In addition, there is a risk of psychological distress associated with the psychological distress survey measures. Additional potential, but not expected, risk is that a supervisor may be

upset about being contacted to participate in a study or may not like the training. Leaders can discuss these issues at any time with research staff.

Risk management and emergency response:

To mitigate potential distress related to the psychological well-being survey items, participants will be made aware that participation is completely voluntary and that they are welcome to not answer any questions participants find distressing or to withdraw involvement at any moment without consequence. On the information sheet, we will provide contact information for behavioral health resources at OHSU.

Confidentiality:

Several processes are put in place to mitigate against breach of confidentiality for survey and training data:

- All devices that can link to OHSU or house OHSU data are required to have Symantec Whole Desk Encryption software installed. All data will be stored on secure, password protected servers.
- Methods of sharing data will NOT include the use of email or thumb drives, but rather by IRB approved methods, such as OneDrive, which is sanctioned by OHSU's IRB.
- If we collect any contact information, including mailing address, email and phone numbers for participants will be kept separate from any files containing survey data. We will only have this contact information from department heads. Only a few key staff members will have access to these files with contact information.
- If there is a reasonable expectation of child abuse, staff are expected to break confidentiality by reporting this to the proper authorities. This information is included in the Informed Consent.
- In the event we have any hard copies of data, they will be kept in a locked file cabinet in the project office, which is also locked when no one is present.
- De-identified data will be kept indefinitely on the secure servers at OHSU.
- Any contact information for participants will be destroyed at the end of the project.
- The project manager will be primarily responsible for ensuring data are secure and protocols are followed by all approved and trained staff.

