 - We will have a data sharing agreement that details these protocols to ensure the confidentiality and integrity of the data. A signed copy stating they will comply with these protocols must be on file with the project manager before an individual is granted access to data, as well as a valid reason for having access (e.g., a paper proposal).
 - All individuals who will have contact with data and/or participants will have a copy of a record of Human Subjects training on file.

The Study PI will also follow the University's guidelines for reporting any unanticipated events in a timely fashion and consult with compliance specialists at the university on appropriate responses or additional reporting as needed.

b. Potential Benefits to Subjects

For employees, there is no immediate, direct benefit. We expect that when we train leaders in mental health support, we also may enhance employees' psychological health and attenuate

traumatic situations that could lead to negative behavioral health outcomes. We anticipate that the training program serves as a primary prevention intervention that will have a positive impact on individual health behaviors, including psychological health, risky behaviors, and hazardous alcohol consumption. This training intervention will eventually have the opportunity of being extended and implemented more broadly. The study holds great promise for informing the implementation of evidence-based leadership training programs across workplace settings.

12. Multi-Site Coordination (delete if not applicable)

~~Portland State University is a co-investigation site on our grant; [name], PI for OHSU, also has a dual appointment at PSU and [name] is PI for PSU. All research activities will be overseen by OHSU staff, including recruitment, data collection, and training delivery. The PSU IRB is ceding oversight to OHSU's IRB. Any PSU research assistants will go through the same training as OHSU RAs. The PSU team will be working primarily in providing consultation and writing papers.~~

References Cited

Adler, A. B., Bliese, P. D., Pickering, M. A., Hammermeister, J., Williams, J., Harada, C., ... Ohlson, C. (2015). *Mental skills training with basic combat training soldiers: A group-randomized trial. Journal of Applied Psychology, 100*(6), 1752–1764. <http://dx.doi.org.proxy.lib.pdx.edu/10.1037/apl0000021>

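### Section 11a names survey distress as a risk but commits only to help at OHSU, although every participant is an active duty soldier at JBLM

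*Combined protocol and SAP*

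**What the plan says.** Section 11a, under foreseeable risks, accepts that the survey's distress measures may themselves upset respondents. The paragraph on risk management that follows offers three things: participation is voluntary, a soldier may skip items or withdraw, and the information sheet will carry contact details for behavioral health at OHSU. No other source of help for a distressed respondent appears in that section or elsewhere in the protocol.

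Section 4 places the target battalions at JBLM in Washington, and section 5b limits entry to active duty soldiers in those battalions. Section 4 also describes the head of Division Behavioral Health as central to the study's development and to most changes in this version.

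On confidentiality, section 9 states: "If there is a reasonable expectation of harm to self or others, staff are expected to break confidentiality". The matching bullet in section 11a states: "If there is a reasonable expectation of child abuse, staff are expected to break confidentiality". The section 11a list is introduced with "Several processes are put in place to mitigate against breach of confidentiality for survey and training data". Each section says that its statement is in the Informed Consent.

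**The concern.** The plan identifies a risk and then answers it with a resource at the researchers' institution, not at the base where respondents serve. Table 1 includes scales for psychological distress, PTSD symptoms, anger and alcohol misuse. Under section 5e, soldiers give name, rank and unit and complete the survey online through a link. For someone upset by the questions, the written contact details are therefore the plan's main route to help (an inference from the online format). A local behavioral health service is the natural contact to list, and the study already has a working link to it.

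What is at stake is modest: whether a distressed soldier is pointed to help at the place of service. Estimates, power and analysis are unaffected.

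**Working it through.** No arithmetic applies. The check sets the relevant statements side by side.

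**1. Risk and response.**

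| Element | Where | Content |
|---|---|---|
| Risk | 11a, foreseeable risks | Distress arising from the survey measures |
| Help offered | 11a, risk management | Behavioral health contacts at OHSU, on the information sheet |
| Who is at risk | 5b | Active duty soldiers, platoon leader or below |
| Where they serve | 4 | Battalions at JBLM |
| Local partner | 4 | Head of Division Behavioral Health |

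The place of the help and the place of the participants do not match, and the local partner is not used for this purpose.

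**2. Does anything else in the protocol fill the gap?** Each candidate was checked.

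- Skipping items or withdrawing (11a) reduces exposure but points to no help.
- Contact details in 5f are for soldiers with questions; those in section 6 are for withdrawing.
- Talking to research staff (11a) is offered to leaders who are upset at being contacted or dislike the training.
- Reporting of unanticipated events by the principal investigator (end of 11a) goes to the University.
- Section 10 defers a safety-monitoring plan unless the study is judged to exceed minimal risk.
- The section 9 duty binds staff; it gives the soldier no contact.

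None names a JBLM, military or crisis resource.

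**3. The two confidentiality bullets.** Child abuse is the only confidentiality-breaking trigger in section 11a; section 9 uses harm to self or others. The two can apply together, and harm to others can include child abuse. Section 11a contains no words that replace or narrow section 9. Read together, the sections leave staff bound to act on expected self-harm. The difference is one of duplicate wording.

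**4. Source of contact details.** Section 11a says "We will only have this contact information from department heads", where section 9 names platoon leaders and unit POCs. The section 11a bullet is conditional on such details being collected at all. This is a clerical misfit.

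**The case against.** The strongest reply is that the contacts are to appear on the information sheet, which was not among the documents. The protocol promises OHSU contacts without saying they are the only ones, so the sheet may already list local services. Nor do the documents say that soldiers cannot use OHSU's resources. A resource outside the chain of command is also a defensible choice, since sections 5e and 4-month follow-up procedures have survey access reported to Battalion POCs. Local behavioral health input was present in the study's development, and section 5d has study materials going to the JBLM IRB.

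Much of this stands. It shows that OHSU should stay on the list and that no harm has been demonstrated. It does not show that the protocol commits to any help at the base. Neither the partner's involvement nor the JBLM IRB's receipt of materials shows that this sentence was considered.

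A reader might infer from the two confidentiality bullets that staff have conflicting duties, or that a soldier at risk of self-harm falls outside the reporting rule. The documents do not support that: section 9 applies throughout, and one consent form can carry both triggers. Nor do they show where the section 11 wording came from, so its misfits are no evidence that the safeguards were meant for another population.

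**Conclusion.** The point holds as a minor improvement to participant safety. The protocol names a distress risk for soldiers at JBLM and commits only to contacts at OHSU. That text comparison is secure.

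Its reach is everyone who takes the survey, which section 4 puts at a target of 1560 soldiers. The number who would be distressed or would use a local contact cannot be estimated, because the documents give no rate. There is no effect on Hypotheses 1 to 4.

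The conclusion assumes that the information sheet adds nothing to what the protocol promises. If the sheet already lists JBLM resources, only the protocol sentence needs correcting. A reader might go further and infer that soldiers lacked information or access to care at the base. The documents do not support this: they are silent on the content of the sheet and on the services soldiers could otherwise reach.

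The differences between sections 9 and 11a are optional tidying and add nothing to the severity.

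**What to change.** Replace the help sentence in section 11a with one to this effect: *Both the information sheet and the closing page of every REDCap survey will list how to reach behavioral health services at JBLM as well as at OHSU.* Keeping OHSU preserves an option outside the soldier's own command. Keeping the information sheet covers those who stop before the last page.

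The cost is a small amendment that would ordinarily go to the OHSU IRB, with the revised materials also sent to the JBLM IRB; agreement on the contact with Division Behavioral Health; and one REDCap end page. The sample size and analysis do not change.

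Timing limits the benefit. The Timeline in section 4 anticipated an end date of 14 September 2022, and this version is dated 12 October 2022. If both surveys are complete, the change helps only later use of the training, such as the translation to other branches and first responders under Specific Aim 5.

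Optionally, in the same amendment, give section 11a the section 9 trigger, stated to include child abuse, and take its source of contact details from section 9 as well.
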